### 1. Peer Mentoring

During the 6-weeks of the intervention, the program will have weekly breakout sessions for participants to join within the Facebook group. Each week, the counselor and/or study staff will schedule a 45-minute event within the Facebook group that will allow participants to RSVP to, if they so wish. When they click on the event on the day/time it was scheduled for, they will be brought to a video chat room within Facebook where everyone who joined can video chat together. The counselor and/or staff member will be leading each group. Each week will be based on a topic around achieving a healthy lifestyle (or barriers to achieving a healthy lifestyle). The participants will pick the topic for each week. In the beginning of each breakout session, the participants will introduce themselves. Then, the counselor will pose discussion questions related to the topic of the week to facilitate a discussion. The participants will then respond to questions and can take notes. At the end, the counselor will review the top solutions/responses that came up. The meeting will be recorded and posted in the Facebook group for those who missed. Facebook requires all attendees in the event to confirm they are okay with the recording. If they do not wish to be recorded, they will be able to leave the meeting and watch the video after it is posted in the group. The breakout sessions are optional. The point of these breakout sessions is for group members to peer mentor each other, connect on a topic, do some brainstorming, and get to know each other better.

### 2. Facebook Group

Participants will be asked to join a private Facebook group where they will receive weight loss counseling based on the Diabetes Prevention Lifestyle Intervention (DPP). The group leader will counsel participants toward achieving and maintaining the exercise and diet goals to lose weight.

The participants will also be asked to participate in the Facebook group by reading and engaging with the posts from the counselors. Additionally, they will be asked to engage with their fellow participants through comments, reactions, and posts. By interacting with other participant's, they will be able to exercise the peer mentor training that they receive prior to the start of the intervention. The participants will be able to privately message their counselor if they do not want to share something with the group. A detailed description of the how the Facebook group will operate is below.

The counselor will post twice a day in the private Facebook group. Each week's content is based on the corresponding module of the traditional, in-person DPP (<https://www.cdc.gov/diabetes/prevention/lifestyle-program/curriculum.html>). The DPP assigns participants the goals of calorie tracking to achieve a calorie goal based on amount needed to lose 1-2 pounds per week, developing a healthy diet consistent with the American Heart Association guidelines, engaging in 150-300 minutes per week of moderate intensity exercise (i.e. brisk walk at 2.5-4 mph, bicycling, gardening, dancing, water aerobics, canoeing, playing doubles tennis, etc.), developing a strength training regimen consistent with the National Exercise Guidelines, and losing 1-2 pounds per week. Goal setting happens on Mondays when the counselor posts asking participants to share their diet and exercise goals with the group. The counselor will suggest 2-3 goals each week—a behavioral goal (e.g., self-monitoring, slip tracking, problem solving), a diet goal (e.g., reduce added sugar) and an exercise goal (e.g., add 15 minutes of moderate intensity exercise on 3 days) to help participants progress toward the overall program goals. Weigh-ins happen on Fridays when the counselor posts asking participants to reply with their weight change in pounds for the week. This ensures participants are weighing themselves weekly and allows an opportunity for problem solving for participants not losing weight. Goal accountability happens each Sunday when the counselor posts asking participants to report how they did on the weekly goals. In between these key posts are posts related to the topic of the week (e.g., nutrition, making time for exercise) and posts relevant to the behavioral strategy of the week (e.g., slip tracking). On the first day in the group the counselor will post a 5-minute problem solving video that teaches the process of problem solving, how the online weight loss program will help them implement this process, and their responsibility as a peer mentor. Additionally, the coach may post periodic videos of themselves or study-related content to facilitate with building a relationship with the participants and to assist with stimulating engagement.

### **3. Mobile Apps**

Participants will be instructed to track their diet and exercise using MyFitnessPal for the first two weeks to achieve a negative energy balance at a level that produces 1-2 lbs of weight loss per week. They will then switch to the slip tracker within the Habit app for two weeks to gain an understanding of their diet and exercise slips and the contextual factors driving those slips. After that, they will then switch to the problem solver within the Habit app for the final two weeks to solve the problems they observed during slip tracking. This schedule was selected to avoid app fatigue and to give participants time to focus and practice each behavioral strategy without getting overwhelmed. However, if participants want to use the other features on unassigned weeks they may do so.

#### MyFitnessPal

Participants will be given a calorie goal based on their BMI, gender, and activity level to produce a weight loss of 1-2 lbs per week. They will be asked to use MyFitnessPal to enter all of the food and beverages they consume and their exercise with the purpose of staying under the calorie goal.

### Habit App.

**Slip Tracking Feature.** The slip tracker helps participants identify triggers of diet and exercise lapses that they can address with the problem solver. For diet slips, the user hits a button when they have a trigger and/or slip and then completes stress and hunger ratings and enters foods eaten and what they were doing at the time. At the end of the day, the user receives a notification asking if they missed recording any slips to ensure all slips were recorded. There will also be an exercise slip tracking feature. It will work such that at the beginning of the week, participants are asked to mark the days they plan to exercise on a calendar in the app. Then, the end of the day notification will ask the user if they exercised that day. If they did not exercise it counts as a slip and they will be asked to pick a day to reschedule. The user will also be asked the time they had planned to exercise and the activity that occurred instead (e.g., sleep, work, sedentary leisure activity). When participants browse their Exercise Slip History they can look for patterns in terms of when they are likely to skip exercise, the role of stress and poor sleep, and which activities they tend to do instead of exercise. This provides insights into what is obstructing their exercise intentions.

**Problem Solving Feature.** Participants will be asked to do problem solving on Mondays of the assigned weeks. Once the user selects diet or exercise on the home screen, the next screen will ask them to identify a problem and then they will answer 3-4 questions before receiving tailored solutions. Once a solution is selected, they will schedule days and times to try it.

**Weekly Check-ins.** The weekly check-in is part of the problem-solving feature. Participants report their weight and if they accomplished scheduled solutions. They can continue working on original solutions and/or to select new ones. Those wanting new solutions are brought to the list of solutions. Participants who lost no weight will be prompted to try a new solution. Participants who have lost no weight but have accomplished their solutions will be prompted to select a new problem to work through. This will prevent participants from putting more energy into solving problems that are not resulting in weight loss and to nudge them toward problems that are obstructing weight loss. If a participant hasn't lost weight and has not executed their chosen solutions, they will be prompted to change the scheduling of the solution or to change the solution. This will help dislodge participants who are stuck. It might also prevent them from abandoning the app when a plan isn't working by guiding them on what to do when stuck. The essence of problem solving is to keep iterating solutions until something works, so the app, like a therapist, keeps the participant moving through that process.

## **4. Mobile App Integration with the Facebook Group**

**Problem Sharing in the Group.** When participants select a problem from the app but do not find a desirable solution, the app will provide an option for them to share the problem in the Facebook group. The prompt will provide language the user can edit as she/he sees fit: "*I am working on [night time snacking]! I welcome ideas! Thanks!*" If so much problem sharing occurs in the Facebook group that it overwhelms the feed in the pre-pilot, we will place a limit on how often the app allows the user to share a problem.

**Sharing Plans to Implement Solutions in the Group.** Participants can also share their chosen solution with the Facebook group by clicking a button that brings up a dialogue box to edit: "*I plan on [bringing my lunch to work] this week. My reminders are set for [7pm Sunday – Thursday]. Ask me how I'm doing this week!*"). Making a commitment in the group increases

accountability. To prevent the feed from getting flooded with such posts, the app will only allow the user to share one plan per week.

**Sharing Successes in the Group.** In the Habit app, when participants have successfully solved a problem and lost weight, they will have the opportunity to click a button to share to the Facebook group.

## 5. Weigh-ins.

Participants will receive a Fitbit Aria scale mailed to them by the study team. This will allow them to take their weight weekly and at assessments. Weight is logged directly from the scale to the Fitbit app. Using a Wi-Fi scale will allow for a standard weight measure for each participant with a higher level of accuracy than self-reported weight. Weight is logged directly from the Fitbit scale to the participants' Fitbit account. Participants will be asked to set up a Fitbit account for the study and share login with the study staff so that the staff can record the weight taken. Study staff help the participants set-up their Fitbit scale if they need it and check their BMI once the scale is working. If a participant has a BMI under 25, we exclude them from the study, and allow them to keep their scale as compensation. At the end of the study participants will be allowed to keep their scale and instructed to change their Fitbit password. If they already have a Fitbit account and choose not to create a 2nd one for the study, they may choose to share that login with the study staff. If they choose not to share their login for the duration of the study, they will be allowed to upload screenshots of their weight to a secure REDCap link. Study staff will delete the screenshot from REDCap once the weight has been logged into the record.

**Follow-ups.** Follow-ups are completed after the intervention ends. Participants will receive a link to an online REDCap follow-up survey during the 7th week after the start of the intervention. This survey will be a repeat of some of the measures assessed at baseline (indicated in the measures table below) and questions to solicit participants' feedback on the program and app. The participants will also weigh-in one final time during the 7th week. Finally, the participants will schedule and attend a focus group call lead by study staff to get their feedback on their experience in the intervention.

**Adverse Events.** Adverse events will be documented during the intervention and follow-up phases. AE's will be formally assessed at follow-ups by asking a question in the REDCap survey. During the intervention AE's will be documented when a participant reports it to the weight loss counselor or posts in the Facebook group. If it is reported during the intervention, the counselor will notify [name] at UConn within 24 hours of learning of the event. UConn will then report it to the IRB (immediately if it's serious, or at the time of annual renewal). If participants gain 5% or more weight during the intervention, this will be treated as an adverse event. The participant will receive a phone call from a UConn RC and they will be asked questions about what might be going on with their weight gain. We will also re-assess Binge Eating Disorder (BED) at this time. If BED is present, we will treat it as a study-related AE. We will only reassess BED once after the telephone screening, even if there are multiple AE's for weight gain. Participants will not be removed from the intervention if they have 5% or more weight gain.

[Describe study procedures for use of interviews or focus groups if applicable. Include details such as how long each procedure will take to complete, who will be asked to participate in these procedures and where these procedures will be conducted. Provide copies of interview and focus group questions/topic areas.]

**Focus groups.** A focus group will occur in a WebEx setting starting in the 7th week after the start of the intervention. The focus group will last for approximately 60 minutes and will include a discussion about likes and dislikes of the intervention. All focus groups will be conducted via WebEx including 1-4 participants on each call. Any participants who are unable to attend the

focus group will receive the focus group questions through an e-mailed survey. We will e-mail the survey twice. At the time of the 2nd e-mail, we will also call them to let them know to check their e-mails. If there is no response from the participant after the 2nd e-mail, we will make no further attempts to contact them. The focus groups will be recorded on WebEx and then will be transcribed using Otter.ai, a web-based transcription software.

After the study is over, we will be removing all members and all content from the Facebook group.

[If the study includes *measures, survey instruments and questionnaires (including the collection of demographic data)*, identify each and, if available, provide references for the measures. Describe what they intend to measure (relate to purpose/hypothesis) and their psychometric properties (e.g., reliability and validity). Identify any that were specifically created for the study and attach a copy for IRB review.]

See below.

Data Collected	List of Measures	Baseline	6-week usability	F/up	Method
Inclusion/Exclusion criteria	Initial screening survey*	X			REDCap or Qualtrics
BMI	Height	X			REDCap
	Weight	X		X	REDCap
Demographics	Income, employment, marital status, race/ethnicity, household composition*	X			REDCap
Binge Eating Disorder	SCID Eating Disorder Examination Questionnaire 	X			REDCap
Depression	Patient Health Questionnaire (PHQ-8  )	X			REDCap
Weight Loss Problem Solving Skills	Social Problem Solving Inventory-Revised (Modified for weight loss)	X		X	REDCap
Problem Sharing and Peer Mentoring	Facebook Engagement		X		Grytics into REDCap
App use	App use data*		X		WPI server and REDCap
Diet tracking	Data extraction*		X		MFP records
Usability Feedback	Acceptability, satisfaction, burden*, and user engagement			X	REDCap and interview

\*investigator derived

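### Apart from weight gain of 5% or more, no solicited adverse-event question is described before week 7, so an unvolunteered event may reach staff up to about 6 to 7 weeks late

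*Combined protocol and SAP*

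**What the plan says.** The protocol describes two ways of learning about adverse events.

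- **During the 6-week intervention (Adverse Events):** "During the intervention AE's will be documented when a participant reports it to the weight loss counselor or posts in the Facebook group". The counselor then has a deadline, which runs "within 24 hours of learning of the event".
- **After the intervention (Adverse Events):** "AE's will be formally assessed at follow-ups by asking a question in the REDCap survey". The Follow-ups paragraph gives the timing: "Participants will receive a link to an online REDCap follow-up survey during the" seventh week from the start.

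One kind of event does not depend on a report. A gain of 5% or more in body weight counts as an adverse event and triggers a call, and weigh-in submissions are checked weekly (Data Safety Monitoring, item 1).

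Under Data Safety Monitoring, item 5 commits the team to assess and record events during the intervention and to follow them to resolution, with prompt review by the program director. The adverse-event part of item 3 promises a listing that includes duration, severity and relatedness.

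**The concern.** The response steps (counselor notice, program director's review, immediate notification of a serious event) start only when staff know that something has happened. Exercise injury is the first risk named under Potential Harms/Risks and Inconveniences, and participants take part remotely, so no clinic visit would reveal one. If a participant hurts a knee in week 1 and does not mention it, the first described occasion on which the study asks is after the intervention has ended. Follow-up to resolution can then no longer be prompt, and the onset and duration in the final listing rest on memory.

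**Working it through.** **Step 1: is there an earlier solicited question?** The other contacts in weeks 1 to 6, as described:

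- Sunday post (Facebook Group): "Goal accountability happens each Sunday when the counselor posts asking participants to report how they did on the weekly goals". It asks about goals.
- Private messages (Facebook Group): "The participants will be able to privately message their counselor if they do not want to share something with the group". This is a channel, not a question.
- Breakout sessions (Peer Mentoring): "The breakout sessions are optional", with topics chosen by participants.
- Slip tracker (Habit App): "Then, the end of the day notification will ask the user if they exercised that day". It asks about exercise done, and the feature is assigned for 2 of the 6 weeks.
- Weekly check-in in the problem solver: weight and completion of planned solutions.
- Weekly app-usage survey (Participant Time table): 5 minutes in each of 6 weeks. Its items are not given.

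Any of these could bring an injury to light, but none is described as asking about health events. The measures table has no adverse-event row. The count of described solicited questions in weeks 1 to 6 is therefore 0. With one weekly item it is up to 6 (1 versus up to 7 when week 7 is included).

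**Step 2: how long is the delay?** The plan states no recall interval, so there is no figure to reproduce. Inputs: the intervention lasts 6 × 7 = 42 days, and the follow-up survey is answered between day 42 (start of week 7) and day 49 (end of week 7). Let t be the time of the event in days.

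- As written: delay = 42 − t, plus a response lag of 0 to 7 days.
- With an item at the end of each week w: delay = 7w − t, plus the same lag of 0 to 7 days.

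| Event in | As written, no lag | As written, 7-day lag | Weekly item, no lag | Weekly item, 7-day lag |
|---|---|---|---|---|
| Week 1 | 35–42 days | 42–49 | 0–7 | 7–14 |
| Week 3 | 21–28 | 28–35 | 0–7 | 7–14 |
| Week 6 | 0–7 | 7–14 | 0–7 | 7–14 |

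With equal lag on both sides, the time saved is 42 − 7w days: 35 for week 1, 21 for week 3 and 0 for week 6. Counting whole calendar days instead (events on days 1 to 42, survey on day 43 to 49), the longest delay is 43 − 1 = 42 to 49 − 1 = 48 days. If events are spread evenly over the 42 days (an assumption), the mean on that count is 21.5 to 27.5 days.

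**Step 3: withdrawal.** Under the conditions for removal, a participant may leave the intervention but keep the final assessment, or leave with no further contact. Only the second choice removes the week-7 question. Each such person is 1/20 = 5% of the sample. The plan gives no withdrawal rate, so this is one person's share and not an expected loss. With the weekly item, someone leaving after week k would have up to k solicited answers.

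**Step 4: burden.** At an assumed 1 minute per week, 6 × 1 = 6 minutes. Against the tabulated total of 5 + 15 + 90 + 930 + 95 = 1,135 minutes, that is 6/1,135 = 0.5%.

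**The case against.** The case for leaving the plan alone has real substance. This is a one-arm usability pilot of 20 people with no statistical comparisons, and the reporting method is stated openly. Participants must be regular Facebook users to be eligible, and the group is checked daily, so the sample is chosen for using the reporting channel. Participants are told to get medical help for pain, which does not depend on staff knowing. Those who report discomfort are referred to their primary care provider, conditions that predispose to injury are screened out, and the protocol rates injury as unlikely. Item 5 of Data Safety Monitoring also mentions a separate standard protocol for safety procedures, which may hold more detail. All of this stands and limits the size of the point. None of it describes a solicited question before week 7.

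Four stronger readings are tempting, and the documents do not support them.

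- *Unvolunteered events are lost.* The week-7 question can still capture them from anyone who answers, and reminders and payment after follow-up encourage answering. For those participants the issue is delay and recall.
- *People who withdraw completely are never asked.* The protocol bars later contact, but it does not say what is asked when the withdrawal options are offered.
- *The plan breaks its own promise to assess and follow events.* That commitment can fairly be read as covering events staff know about.
- *Oversight of ordinary events is held up.* Non-serious events go to the IRB at annual renewal, and the safety officers receive the data report after follow-ups are complete. Earlier capture would change neither timetable.

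**Conclusion.** The point holds as a limited design weakness. Apart from weight gain of 5% or more, capture in weeks 1 to 6 depends on volunteering, and the one described solicited question comes in week 7. Recall can reach about 6 to 7 weeks for an event at the start of week 1, and it falls to two weeks or less for week 6. The benefit of asking weekly is confined to four things: earlier review and follow-up by the program director, better recall of onset and duration, earlier notice of a serious event nobody volunteered, and some solicited data from people who later withdraw.

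This rests on two assumptions: that the weekly app-usage survey and the separate safety protocol do not already contain such a question, and that the follow-up survey is answered within week 7. It is worth doing because it is cheap. Confidence is medium because the content of that survey is not available.

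**What to change.** Add one item to the weekly app-usage survey: any injury, pain, illness or other health problem since the last survey, yes or no, with free text. Collect it in REDCap so that the existing 48-hour check of submitted surveys applies. Add a sentence to the Adverse Events section saying so; if the survey or the standard safety protocol already asks, that sentence is all that is needed. In the final adverse-event report, list solicited and spontaneous events separately and state how many participants gave no solicited answer.

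The cost is one survey item, about 6 minutes per participant over the study, and some logging of minor unrelated complaints. The item helps only in weeks when the survey is answered, and it cannot reach anyone after complete withdrawal.
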